3.0 Objectives

The overall objective of our mixed method study is to evaluate a strategy to improve the quality and clinical usefulness of 'the 5th Vital Sign' in VA primary care. We will first develop a patient-self administered computer-aided pain assessment, then evaluate and refine the assessment using human-computer interaction laboratory usability testing. Next we will conduct a three site randomized controlled trial (RCT) to test a computer-based pain assessment protocol compared with usual pain screening. In the RCT we will evaluate three arms – one arm will use the PEG, a more sensitive screener including pain functional impairment, and a second arm will replicate the 'NRS now' allowing a direct comparison of patient-administered assessment vs. clinician assessed pain and a third arm will test the NRS at one week. All subjects will be screened with the '5th Vital Sign'. (allowing a three arm comparison of each of two computer based approaches vs. usual practice) Our specific aims are to:

Aim 1. Characterize primary care team perspectives on enhanced pain screening approaches compared with usual pain screening, including clinical usefulness and how to use skills, roles, and tasks of multidisciplinary primary care clinicians and consultants to optimize pain care. Additionally, we will try to understand Veterans' experiences with pain screening, assessment, and management (including use of opioid analgesics) in order to better link their actual experience with provider assessment and management practices. Interviews and focus groups will inform refinement of the items and screening interface; we will evaluate the interface including the PEG and 'NRS now' and the control arm for usability including among disabled veterans and for use in primary care.

Aim 2. Evaluate in a three-arm RCT the effects of enhanced pain screening approaches using a tablet and comparing the PEG, the 'NRS pain now', and usual clinician-assessed pain screening.

Hypothesis 2a: One of three enhanced pain screening approaches using the PEG, but not the 'NRS now' will be associated with improved detection of pain related disability **Hypothesis 2b:** Enhanced pain screening approaches vs. usual pain assessment will be associated with equally low missingness, Veterans, providers, and clinic and facility staff will characterize their experience with the enhanced screening protocol and important barriers, facilitators, and practical steps to inform implementation

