The 1 page field log will contain both identifiable (i.e., Full Name, last 4 digits of SSN, and contact information as needed for participation in follow up interviews) and unidentifiable data (i.e., participation status, participant ID, and observable demographics when necessary, and other research pertinent information). While in the clinic field logs will be kept on person by research staff and in a locking carrying case or secured mail bag to be transferred to a designated office. The paper documents will be stored in a locked filing cabinet inside of a locked office on VA campuses at the designated VA sites (i.e., Palo Alto, Minneapolis, Portland). A designated research assistant from each site will input the data into an encrypted and password protected Excel sheet that is kept on a secured server at VA Palo Alto. The designated research assistants at VA Portland VA Minneapolis will only have access to the cross-walk Excel sheet for their specific site. Research assistants from Palo Alto (i.e., [name] and [name]) will have access to a site specific Palo Alto Excel sheet and a master cross-walk Excel sheet that is populated by site specific crosswalks. Drs. [name] and [name] will have view only access to the master cross-walk excel sheet. At a later stage in the study, a designated programmer will have view only access to the master cross-walk excel sheet in order to compile data from both tablet survey data and medical records.

5. Tablet based survey content:

We will focus on content that is not available in existing VA administrative database the survey will include (not in this order):

- 1) an **introductory screen** which allow for registration using the unique participant number, and
- 2) **an algorithm corresponding to the three intervention arms of the RCT** and an underlying randomization engine to allocate Veterans to the three arms using a random number generator, with the corresponding pain screening measures (PEG, NRS one week, and DVPRS), and
- 3) The **Graded Chronic Pain Scale** (the gold standard for comparison),and
- 4) **Self-assessed level of physical activity**, and
- 5) **expectations and unmet need for pain treatment and management**, and

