- 6) **familiarity and experience with technology and satisfaction with the rating experience** including whether the veteran has previously used a tablet and environmental context because these items reflect previous concepts salient to pain rating variation, and
- 7) **access to and experience with smart mobile technology**

Depending on the consideration of survey length which we will prioritize to keep the survey at approximately 10 minutes, we will consider including several other items that previous research have shown to be important in considering pain outcomes including duration of pain in the previous year and the physical location of pain. In order to minimize survey burden and in order to complete our planned analyses, we will consider using VA data (rather than participant responses to obtain information about BMI, comorbidity, copay exemption status). We will also ensure physical attributes of the tablet screen best accommodate visually impaired and other physically disabled veterans where possible.

At the conclusion of the study in order to assess the degree to which implementation succeeded and Veterans who were missed by the tablet based protocol, we will compare all Veteran patients of the clinic during the study interval, as well as all Veterans who were approached but declined, with all Veteran users of the tablet during the same time by age, race / ethnicity, gender, cognitive impairment and mental health diagnoses, and NRS pain ratings, to assure that the tablet based screening process does not disadvantage any Veterans. We will gather these factors using VA electronic databases and will request a HIPAA authorization and waiver of documentation of informed consent for this portion of the study.

The usual care arm nursing staff rating of the 'NRS pain now' will be collected by linking the encounter to the Vital Signs Package to obtain the pain rating. Veterans' health records accessed in Corporate Data Warehouse and CAPRI/ VistAWeb/CPRS, will inform basic demographics and clinical factors in order to allow us to minimize the burden of the tablet protocol.

B. Patient Follow up Interviews:

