If possible, research staff will attend a local clinic staff meeting to briefly inform the staff of the study. By partnering with local clinic leadership, we plan to send emailed invitations to eligible staff members. A log of all contact attempts will be maintained and after a maximum of 3 contact attempts the staff member will be removed from the contact list.

2. Consent Process:

Prior to the interview, a research staff member will verbally consent the participant. We have approval for a waiver of documentation of informed consent. Date of consent and person obtaining consent will be logged on the secured Excel sheets stored on VA Palo Alto Servers.

3. Data Collection Procedures:

We will conduct up to 40 telephone interviews that will take approximately 20-30 minutes. The interviews will be audio recorded and later transcribed by a VA contracted transcription service. For interview questions/content please see the Provider Interview Protocol.

4. Data Security:

Any information linking identifiable information with an assigned participant ID will be located on the secured Excel sheets. These Excel sheets will be secured and stored as previously mentioned under Phase 2: a: Data Security.

Audio files will be uploaded to the secured server located at VA Palo Alto. The audio Files will be saved using the assigned participant id. Audio files and de-identified transcripts will be transferred between VA servers and the transcriptions service via an approved secured FTP server.

Figure 1: Estimated enrollment scheme for ESP

Due to randomization the proposed enrollment algorithm will allow analytic comparison of each assessment measure / mode to the other. The table below specifies the Arm to Arm comparisons but the outcomes of each comparison are ‘clinically significant pain’ defined as pain that is moderate to severe, pain that is associated with disability, or unmet need for additional management.

Main comparison (s) of interest		Arm (s)	Comment
1	Tablet: PEG vs. NRS 1 week vs. DVPRS	1 to 2 to 3 tablet comparison	Baseline arm to arm difference

Table 1: Main analytic comparisons by screening measure and mode for outcomes of detection of pain, detection of moderate / severe pain (clinically relevant), pain associated with disability and unmet needs for treatment

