5.3 Study Evaluations/Data Analysis

Phase	Data Type	Source	Outcome	Analyses	Comment
1	Qualitative	Multidisciplinary providers, clinic staff, and Veterans	n/a	Grounded theory	Characterize screening information use in care
			management		
1	Quantitative	Patient	Pain-related disability, detection	By intervention arm*	At screening encounter

1&2	Quantitative	Patient, linked to VA health data for Veteran demographics and clinical factors	Pain missingness,	By intervention arm*	At screening encounter
2	Qualitative	Provider, patient	Satisfaction and experiences with screening including implementation	Grounded theory	Characterize experiences with the tablet and enhanced pain screening approaches

Outcome	Measure	Analysis	Model
Immediate pain related disability	NHIS pain-related disability	Arm 1,2,3 pairwise	Linear regression, adjusted for patient factors
Immediate pain missingness	NRS (nurse), NRS (tablet), PEG (tablet);	% missing pain ratings (Arm 1,2,3)	Logistic regression, adjusted for patient, rater (tablet perception), and environmental factors

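### Hypothesis 2b compares missingness on the tablet with missingness at the nurse, but the stated missingness analysis compares randomised arms that are all tablet arms

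*Protocol*

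**What the plan says.** **Hypothesis.** Protocol section 3.0, Hypothesis 2b: "Enhanced pain screening approaches vs. usual pain assessment will be associated with equally low missingness". The comparison is between modes, tablet against nurse.

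**Analysis.** In section 5.3, the row for immediate pain missingness gives the percentage of "missing pain ratings (Arm 1,2,3") with a logistic regression. The first table in that section also says that missingness is analysed by intervention arm. The measures in the row are "NRS (nurse), NRS (tablet), PEG (tablet").

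**Arms.** Section 5.1 (tablet survey content, item 2) randomises on the tablet, "with the corresponding pain screening measures (PEG, NRS one week, and DVPRS"). Table 1 gives one main comparison: "Tablet: PEG vs. NRS 1 week vs. DVPRS". The abstract also has three tablet screeners with the DVPRS as Arm 3, although it calls Arm 2 the NRS for pain now.

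**Nurse rating.** Section 3.0 states "All subjects will be screened with the" fifth vital sign. Section 5.1 obtains that rating by linkage to the vital signs record.

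**Other layout.** Aim 2 in section 3.0 lists the PEG, the NRS for pain now "and usual clinician-assessed pain screening" as the three things compared. Section 5.1 has the phrase "The usual care arm nursing staff rating of the" NRS, as if usual care were an arm.

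**The concern.** A hypothesis and the analysis listed for its outcome should concern the same contrast. Here the hypothesis asks whether moving from nurse to tablet costs pain ratings, and the analysis asks whether one tablet screener loses more ratings than another. A null result from the second says nothing about the first.

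The project is meant to inform national adoption of a screening measure and method. If all three tablet screeners lost ratings at a similar, high rate, the by-arm model would show no difference, and that could be taken as support for equally low missingness.

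The measure list adds doubt about which arms the row has in mind. It names the nurse NRS, a tablet NRS and the PEG, which fits the layout in Aim 2 and not the three randomised tablet screeners.

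**Working it through.** The protocol gives no missingness rate, power or precision for this outcome, so there is no figure of its own to reproduce. The check is first structural, then an illustration on assumed rates.

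**Step 1. What the by-arm model can estimate.** Let pt1, pt2 and pt3 be the probabilities of a missing tablet rating in the three arms, and pn the probability of a missing nurse rating.

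- By-arm model: OR for arm j against arm 1 = [ptj/(1 − ptj)] / [pt1/(1 − pt1)]. It contains no pn. If pt1 = pt2 = pt3, every OR is 1.0, whatever the common value and whatever pn is.
- Using missing nurse ratings as the outcome changes nothing: arms are still compared with arms.
- Hypothesis 2b concerns pt − pn. Both ratings come from the same participant, so this is a paired difference.

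**Step 2. The other reading of the row.** Suppose Arm 1,2,3 here meant nurse NRS, tablet NRS and PEG. That contradicts the abstract, section 5.1 and Table 1, where the arms are three tablet screeners. It would also treat ratings from the same people as separate arms, because every participant has a nurse rating. The row needs correcting on either reading.

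**Step 3. Illustration.** Inputs from the protocol: about 650 participants (section 5.1, recruitment) and 1:1:1 allocation (abstract), so 650/3 ≈ 217 per arm. Assumed: pt = 8% in every arm, pn = 2%, within-person correlation r of the two misses 0 or 0.3.

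SE = sqrt{[pt(1 − pt) + pn(1 − pn) − 2r·sqrt(pt(1 − pt)·pn(1 − pn))]/n}

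- pt(1 − pt) = 0.0736; pn(1 − pn) = 0.0196; sum 0.0932.
- n = 650, r = 0: SE = sqrt(0.0932/650) = 0.0120; 6.0 ± 2.35 points, CI 3.65 to 8.35.
- n = 650, r = 0.3: the covariance term is 0.6 × sqrt(0.0736 × 0.0196) = 0.0228; SE = sqrt(0.0704/650) = 0.0104; CI 3.96 to 8.04.
- n = 217 (one arm): CI 1.94 to 10.06 (r = 0) and 2.47 to 9.53 (r = 0.3).
- By-arm ORs in the same data: 1.0 throughout.

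**Step 4. Precision if tablet and nurse are equal** (r = 0, half-width = 1.96·sqrt(2p(1 − p)/n)):

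| Assumed p | n = 650 | n = 217 |
|---|---|---|
| 2% | 1.5 points | 2.6 points |
| 5% | 2.4 points | 4.1 points |
| 10% | 3.3 points | 5.6 points |

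The paired difference can thus be estimated usefully from data the trial already plans to hold, better overall than within one arm.

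**The case against.** The strongest reply is that the row does list the nurse NRS beside the tablet measures. A plain report of the percentage missing for each measure would show a gap of 8% against 2%, even though an arm coefficient would not. Section 5.1 also says that the design lets each measure and mode be compared with the others. This stands in part: the nurse data are in scope, and a reader who infers that they are ignored, or that Hypothesis 2b cannot be examined at all, goes beyond the documents. But the only contrast stated for missingness is between arms. Table 1 lists only a tablet-to-tablet comparison, and its outcomes concern detection of pain and unmet need, not missingness.

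A second reply is that the choice of paired method, and any margin for calling two rates equally low, belongs in a statistical analysis plan. That is accepted, and the lack of a margin is not counted. The point is that the protocol has already named a contrast, and it does not match its own hypothesis.

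Three stronger inferences are tempting and are not supported:

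- *A third of tablet ratings escape the missingness analysis because the DVPRS is not listed.* Arm 1,2,3 covers the DVPRS arm, so this is a mismatch to reconcile.
- *The row plans a weak comparison of 217 nurse ratings with 217 tablet ratings.* No section plans this. Any power lost that way would come almost entirely from the smaller n.
- *The model is biased because it adjusts for satisfaction with the assigned screener.* The row names only an undefined tablet-perception factor. Satisfaction is one of several survey items that might be meant, alongside technology familiarity, prior tablet use and clinic environment. Any distortion would rest on assumed rates and an assumed arm difference in satisfaction.

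**Conclusion.** The concern holds in this form: the stated missingness analysis compares randomised tablet arms and does not estimate the within-person tablet-against-nurse contrast of Hypothesis 2b. The measure list does not match the three tablet arms either.

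This conclusion is structural and depends on no assumed rate. It rests on two statements in the protocol: that all three arms use the tablet, and that every participant also has the nurse rating. Its size cannot be read from the protocol. In the illustration a real gap of 6 points leaves every arm odds ratio at 1.0, but the 8%, the 2% and the correlations are assumptions.

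The fault is moderate. It concerns a stated hypothesis and a named outcome, but the data needed to repair it are already to be collected.

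**What to change.** In section 5.3, split the missingness row in two:

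1. *Hypothesis 2b.* The paired tablet-minus-nurse difference in the proportion of missing ratings, with a 95% CI, over all participants and by arm. Either a McNemar-type interval or a GEE with mode and mode-by-arm terms would serve.
2. *Between screeners.* Keep the by-arm logistic regression as a separate comparison of tablet missingness across the three arms.

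Add the DVPRS to the measures. Reconcile Aim 2 and the accompanying text in section 3.0, the usual-care wording in section 5.1 and the row in section 5.3 with the three tablet arms, including whether the NRS arm asks about pain now or over one week. When tablet perception is defined, leave satisfaction with the assigned screener out of it, since that is recorded in the same survey and may depend on the arm.

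The cost is wording and slightly more analysis, since the nurse rating is already linked. One limit should be stated with the result: the tablet is completed before contact with the nurse, so nurse missingness here may differ from nurse screening without a tablet.

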5.4 Withdrawal of Subjects

- Veteran subjects will be withdrawn from the research without their consent if they are found to have any physical or cognitive abilities that makes them unable to participate in or tolerate an interview.
- Participants of this study will have the opportunity to opt out of the study at any point in entire duration of the study if they so desire. If a subject decides to discontinue participation, only information collected up to that point will be used, and no additional information will be collected.

6.0 Reporting

- Our procedures for reporting unanticipated problems, serious adverse events, and protocol deviations include immediate notification of the Central IRB, local IRB, and our security officers. Adverse event reports will be executed if necessary.

7.0 Privacy and Confidentiality

- This study will use Veteran subjects' Protected Health Information (PHI).
- Data will be secured in a number of ways:
 - All study staff will have adequate training in data security practices and procedures
 - Access to such data sources will be extremely strict and only granted to those absolutely necessary for project execution
 - Data will be stored on a server protected by the VA's firewall and password protection
 - Tablets will be designed with physical barriers to protect patients privacy

8.0 Communication Plan

- SAEs that have the potential to affect implementation of the study will be communicated to all engaged participating sites. This will be achieved by doing the following: SAEs and other events this serious in nature will be discussed at weekly project meetings involving all sites.
- Study events and interim results (if appropriate) are communicated regularly to engaged participating sites. This will be achieved by doing the following: Study events and results will be communicated at weekly project meetings involving all sites.
- LSIs must conduct the study appropriately. This will be achieved by doing the PI/SC doing the following to ensure adequate monitoring:
 - Weekly conference calls among project leaders and members
 - Review of IRB communications to insure consistency in standards and measures along with critical documents.
 - Data management will be discussed among staff members on a weekly basis.
 - Maintaining study staff log with up to date information about trainings and data access and security.

